#### **4.5 Duration of Study Intervention**

The study intervention is complete once the patient receives their last (8 weeks post-treatment) PET-MRI scan. The patient may be withdrawn from the study prior to this point if any of the following apply:

- Inter-current illness prevents completion of imaging studies
- Unacceptable adverse event(s) prevents completion of imaging studies
- Patient decides to withdraw from the study, **OR**
- General or specific changes in the patient's condition render the patient unacceptable for completion of study in the judgment of the investigator.

#### **4.6 Duration of Follow Up**

Patients will be followed up via review of their medical records through disease recurrence or survival for up to 5 years.

#### **4.7 Removal of Patients from Protocol**

Patients may be removed if they experience unanticipated claustrophobia causing intolerance to the MR. If patients require lorazepam in order to tolerate the MR, they will be withdrawn from study participation.

#### **4.8 Abstraction of Medical Records**

De-identified records will be reviewed and data extracted for clinical outcomes. Treatment response will be documented based on pathology results, as well as any information on recurrence and survival. Information collected may help to establish preliminary data for future studies.

### **5.0 TIME AND EVENTS TABLE**

#### **5.1 Time and Events Table**

	Baseline	Treatment	Mid-	Treatment	Post-	Surgery	Pathology	Long-
--	----------	-----------	------	-----------	-------	---------	-----------	-------

	0 weeks	+0 to +2 weeks	treatment +2 weeks	+2 to +4 weeks	treatment +8 weeks	+8 to +10 weeks	+10 to +12 weeks	term follow-up  >+12 weeks
Screening								
Informed Consent								
Pregnancy test 								
PET-MRI								
Radiation Therapy								
Surgery								
Pathology								

If clinically applicable women of childbearing potential will undergo urine or serum pregnancy test within 7 days prior to baseline scans; urine pregnancy test within 7 days prior to each subsequent PET/MRI.

Long-term follow-up will be restricted to abstraction of medical records for any data on recurrence and/or survival for up to three years post treatment.

## 6.0 EXPECTED RISKS/UNANTICIPATED PROBLEMS

### 6.1 Assessment of Safety

In general, any patient enrolled on this protocol will be evaluable for adverse events.

### 6.2 Expected Risks

#### 6.2.1 Risks of PET/MRI

##### Emotional Distress

Emotional distress is possible during MRI. Technologists will ask subjects, before injection, if they are claustrophobic. Also, technologists will do their best to help comfort any subject who is claustrophobic but chooses to continue, by using a cloth over their eyes or a fan providing cool air to the subject. Technologists will hand subjects a squeeze ball alarm and instruct them to use it in case of any discomfort. The technologist will also inform the subject that he/she is free to stop at any time, for any reason.

### Radiation

Radiation: The PET/MRI scans will expose study participants to controlled amounts of limited radiation. The total dose of radiation from these tests is not anticipated to cause any adverse effects of any significance over that which they may experience over their standard of care diagnostic imaging and subsequent therapies. Patients enrolled in this pilot study will receive an estimated dose of radiation as specified by the Radiation Safety Committee. The amount of risk to this estimated dose will be equated to the annual radiation exposure limit for radiation workers in the informed consent. This radiation exposure involves a small risk and is necessary to obtain the information desired.

This research study involves exposure to radiation from radiotracer used for PET/MR scan. The radiation dose subjects will receive in this study is 1.32 rem for each scan for a total of 3.96 rem for the full set of three scans. For comparison, a person in the United States receives a radiation exposure of 0.3 rem per year from natural background sources. The radiation dose that subjects will receive in this study is equivalent to the radiation exposure that everyone receives in 13.2 years from natural background radiation for participants completing three scans. For comparison, the people who work with radiation (radiation workers) are allowed to receive a radiation dose of 5 rem per year. The amount of radiation exposure received in this study is equal to 79 % of the annual radiation exposure limit for radiation workers. This radiation exposure involves only a small risk and is necessary to obtain the research information desired. The radiation exposure described here is what subjects will get from this research study only. It does not include any exposure subjects may have received or will receive from other tests outside of this study that are a part of their medical care.

### FDG

Information about FDG F18 was obtained from the Prescribing Information (August 5 2004); <http://www.accessdata.fda.gov/scripts/cder/drugsatfda/>. According to this document , reviews of the oncology literature did not reveal reported adverse reactions when using 18F-FDG as a diagnostic in conjunction with PET. In a subset (n=42) of a safety database of epilepsy patients (n=374), 4 patients had transient hypotension, 6 had hypo- or hyperglycemia and 3 had transient increases in alkaline phosphatase.

### Gadolinium

An extremely rare disease called Nephrogenic Systemic Fibrosis (NSF) is associated with the use of gadolinium contrast agents in patients with chronic severe renal insufficiency or renal dysfunction due to hepato-renal syndrome or in the peri-operative liver transplantation period. Exclusion criteria for this study are in compliance with the Food and Drug Administration's advisory statements, and patients with creatinine clearance < 30 ml/min will be excluded from this study.

As part of the MRI procedure subjects may receive a dye called gadolinium. Gadolinium makes it easier to see details on the MRI pictures. If subjects have any

problems with their kidneys, they may be at risk for a condition called Nephrogenic Systemic Fibrosis (NSF) or Nephrogenic Fibrosing Dermopathy. NSF has been reported to occur between 2 days and 18 months following injection of gadolinium. There is no known treatment for NSF. Some people have even died from this. Signs and symptoms of NSF may include: burning, swelling, hardening or tightening of the skin, blood vessels and internal organs (heart, lungs, liver; yellow spots on the white part of the eyes; joint swelling and stiffness; pain in the hip bones or ribs; muscle weakness.

Subjects' study doctor will check how well their kidneys work before they are given gadolinium. Depending on how well their kidneys work, they may be given a reduced dose or they may not be able to take gadolinium at all. NSF has not been reported in people with normal kidneys.

### **6.3 Unanticipated Problems**

#### **6.3.1 Definition**

As defined by UNC's IRB, unanticipated problems involving risks to study subjects refers to any incident, experience, or outcome that:

- Is unexpected (in terms of nature, severity, or frequency) given (a) the research procedures that are described in the protocol-related documents, such as the IRB-approved research protocol and informed consent document; and (b) the characteristics of the subject population being studied;
- Is related or possibly related to a subject's participation in the research; and
- Suggests that the research places subjects or others at a greater risk of harm (including physical, psychological, economic, or social harm) related to the research than was previously known or recognized.

#### **6.3.2 Reporting**

Any unanticipated problem that occurs during the conduct of this study and that meets **at least** the first two criteria listed in 6.3.1 must be reported to the UNC IRB using the IRB's web-based reporting system.

## **7.0 STATISTICAL CONSIDERATIONS**

### **7.1 Study Design/Study Endpoints**

The purpose of the study is to assess the utility of combined, simultaneous positron emission tomography (PET) and magnetic resonance imaging (MRI), collectively called PET-MR, in assessing response to neoadjuvant radiation therapy in the treatment of high grade sarcomas. The overall design is to image patients with PET-MR at three time points, pre-treatment, mid-treatment, and post-treatment, and correlate quantitative measures from imaging with results of pathology to determine if the mid-treatment PET-MR scan provides information that predicts response to radiation therapy. The primary endpoint is to quantify the association between

pathology determination of response/nonresponse and image metrics from PET at midtreatment. Exploratory aims will address the development of a prediction model for response mid-treatment change in PET and MR, and will evaluate the use of combined PET and MR metrics for prediction compared to each metric alone.

Patients will be identified at the Multidisciplinary Sarcoma Board at UNC. Patients will be high-grade sarcoma patients that are to be treated with neoadjuvant radiation therapy followed by curative intent surgery. Once patient identification occurs, the patient will be assessed for the study via the inclusion and exclusion criteria mentioned above. The patient will then be approached by either the PI, the sarcoma nurse navigator, the radiation oncologist, the surgeon, or a member of their team and the study protocol explained and all risks outlined. If the patient provides informed consent the patient will be enrolled. Demographic data such as patient age, gender, comorbidities, and previous treatments, etc. will be collected. Tumor characteristics such as tumor subtype, grade, Ki-67 score, size, invasion into adjacent organs, etc. will be collected. All data collected will be kept on a password protected, secured server, and all physical documentation will be stored in a locked cabinet. All data will be collected by the PI and co-investigators.

Patients will then be scheduled for a pre-treatment PET/MR and proceed to neoadjuvant radiation therapy per the direction of the radiation oncologist. At the end of the second week of radiation therapy the patient will undergo a mid-treatment PET/MR. The patient will complete their radiation therapy. Four weeks after radiation therapy the patient will undergo a post-treatment PET/MR, and proceed for curative intent surgery at 6-8 weeks post radiation if they are still surgical candidates.

For all PET scans, patients will be instructed to fast, and blood glucose levels will be measured prior to imaging. Patients will be injected with 12 mCi 18-FDG, and then imaged starting 60 minutes post-injection for ten minutes each at one or two bed positions focused on the primary tumor site. MRI sequences to be run will include conventional anatomic T1- and T2-weighted sequences, high-resolution T1 pre- and post-contrast sequences, and the Dixon PET-MR attenuation-correction sequence.

The PET/MRs at each time point will be evaluated by UNC radiologists as to the size of the lesion, the FDG activity as measured by tumor-maximum and tumor-mean standard uptake values (SUVs), the presence or absence of invasion to adjacent organs, and the presence or absence of metastatic or multifocal disease. PET images will be evaluated with aligned anatomical MRI for guidance as well as determination of the tumor margins for computation of tumor-mean SUV.

The UNC surgeons will record the resectability of the tumor, and the gross appearance of the resection (R0-grossly negative, R2-grossly positive), as well as any evidence of metastatic disease, presence or absence of invasion to surrounding organs, or multifocal disease. The PET/MRs will be evaluated by UNC radiologists as to the size of the lesion, the FDG activity as measured by SUVmax and SUVmean,

the presence or absence of invasion to adjacent organs, and the presence or absence of metastatic or multifocal disease. The pathological specimens will be evaluated by a UNC pathologist specialized in sarcoma as to the degree of necrosis (none, <10%, 10-50%, 51-90%, >90%, 100%), status of margins (R0-negative margins, R1-microscopically negative margins, R2 – grossly positive margins), the presence and absence and number of affected lymph node involvement if applicable, and presence or absence of invasion to adjacent organs. Again, all data will be stored on a secured, password protected server.

## 7.2 Sample Size and Accrual

The study will enroll 30 eligible patients that are being treated at UNC Hospitals. To test for a difference in change scores between response groups at a given time point (for example, mid-treatment change from pre-treatment) we will utilize the non-parametric Wilcoxon Rank Sum test. An advantage of using this nonparametric method is that the effect size is expressed in probabilistic terms, since the difference scores have been transformed into ranks, the statistical comparisons take place in this space, and the magnitude and variability of the difference scores are not needed. This means the power and sample size for each time point's difference scores will be the same.

Let  $X = x_1, x_2, \dots, x_n$  represent a sample of size  $n$  difference scores for responders and  $Y = y_1, y_2, \dots, y_n$  represent a sample of size  $n$  difference scores non-responders. Now let  $p = P(X > Y)$ , or the probability that a difference score in the responder group greater than the difference score in the non-responder group. Please note that we could just as easily frame the probability  $p = P(Y > X)$ . Intuitively, one can see that a  $p=0.5$  would mean that either  $X > Y$  and  $Y > X$  would be equally likely. This  $p$  would be the measure of the nonparametric or distribution-free effect size. The Wilcoxon signed-rank method tests the null hypothesis that the distributions of the two samples are equal, which corresponds to a  $p=0.5$ .

Assuming 30 patients complete the study, we will have approximately 90% power assuming  $p = 0.82$ , with a Type I error rate of 0.05 and utilizing the Wilcoxon Rank Sum test [1] to test for a difference in PET mean SUV from pre-treatment to mid-treatment. For correlating the fractional change in PET mean SUV with change in MRI tumor volume between time points, with  $n = 30$  subjects, we will have approximately 82.5% power to detect a Pearson correlation of at least 0.5, assuming a two-sided Type I error rate of 0.05 and utilizing the correlation test.

[1] Noether, G. E. (1987). Sample size determination for some common nonparametric tests. *Journal of the American Statistical Association*, 82(398), 645-647.

## 7.3 Data Analysis Plans

Quantitative imaging measures (mean SUV, maximum SUV, MRI-based tumor

volume) will be compounded for all patients. Difference scores including the fractional change from pre-treatment to mid-treatment (early response) and the fractional change from pre-treatment to post-treatment (late response) will be computed for all quantities. Subjects will be classified into responders and non-responders on the basis of degree of necrosis (>90% necrosis = good response; <90% necrosis = poor response). Median, range, mean, and variance of each image measure will be computed for each response group. Differences in all quantitative measures between the response groups will be assessed with the non-parametric Wilcoxon Rank Sum test, and correlations between quantitative measures will be determined using the non-parametric Spearman's rank correlation coefficient and Pearson product-moment correlation coefficient. To develop a predictive model for early response, we will train a logistic regression classifier on the binary response data utilizing various PET SUV and MRI-based imaging measures (in terms of change from pre-treatment to mid-treatment) as covariates. All subsets selection with BIC will be used to determine the best combination of PET and MRI imaging measures to predict binary response, and empirical measures of predictive performance such as leave-one-out cross validation and Receiver-Operating-Characteristic (ROC) curves (evaluated as to the area under the ROC curve) will be computed.

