## **2.0 STUDY OBJECTIVES/AIMS AND ENDPOINTS**

### **2.1 Primary objectives**

- 2.1.1** Determine whether there is a significant difference between response groups in PET mean SUV fractional change (baseline to mid-treatment).

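### Baseline mean SUV is neither a covariate nor a comparator in Section 7.3, so no planned analysis can show whether the mid-treatment scan adds to the pre-treatment scan

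*Combined protocol and SAP*

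**What the plan says.** The primary objective (Section 2.1.1) is worded as a group comparison: "Determine whether there is a significant difference between response groups in PET mean SUV fractional change (baseline to mid-treatment"). Section 7.3 forms the two groups from the degree of necrosis in the resected tumour and gives the test: "Differences in all quantitative measures between the response groups will be assessed with the non-parametric Wilcoxon Rank Sum test".

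The exploratory logistic model for early response in Section 7.3 takes PET and MRI measures "in terms of change from pre-treatment to mid-treatment) as covariates". Baseline values are not listed as candidates, and no baseline-only model is planned.

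Section 7.1 has radiologists record mean and maximum SUV at each time point, so baseline mean SUV will be in the dataset. The same section states the aim, which is to "determine if the mid-treatment PET-MR scan provides information that predicts response to radiation therapy". Sections 1.1 and 1.3 describe the possible future use: a mid-treatment scan that informs whether neoadjuvant radiation continues.

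**The concern.** Fractional change in mean SUV is (mid − baseline) / baseline. If tumours that start with high uptake tend to change by a different fraction from those that start low, the change score carries information that the pre-treatment scan already held. The response groups are formed by pathology after surgery, not by randomisation, so nothing balances baseline SUV between them.

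When both conditions hold, responders and non-responders can differ in fractional change only because they differed at the start. The primary test would be significant although the mid-treatment scan added nothing. The planned prediction model cannot reveal this either, because baseline SUV is not among its candidates.

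Section 1.3 makes the mid-treatment session the one additional PET/MR that the study imposes, and Section 6.2.1 puts each scan at 1.32 rem. What that scan adds to the one before it is the question a later trial would need answered. Section 1.1 says the results may supply effect sizes for such a trial, and an effect size that partly reflects baseline uptake could mislead its planning.

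**Working it through.** **Inputs from Section 7.2.** "Assuming 30 patients complete the study, we will have approximately 90% power assuming" p = P(X > Y) = 0.82, "with a Type I error rate of 0.05 and utilizing the Wilcoxon Rank Sum test". Both groups are written with the same n, which implies 15:15. No responder rate is given. Sidedness is stated only for the correlation test ("assuming a two-sided Type I error rate of 0.05 and utilizing the correlation test"). I take the primary test as two-sided too.

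**The plan's own figure.** Noether's formula: power = Φ(√(12·N·c·(1−c))·|p − 0.5| − z).
- With N = 30, c = 0.5, p = 0.82: √(12 × 30 × 0.25) × 0.32 = √90 × 0.32 = 3.036.
- Two-sided: Φ(3.036 − 1.960) = 85.9%.
- One-sided: Φ(3.036 − 1.645) = 91.8%.
- Simulated two-sided rank-sum test, normal shift √2·Φ⁻¹(0.82) = 1.29 SD, 15:15: about 91%.

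The stated 90% or so is matched by simulation, and by Noether one-sided. The simulations below start from the same point.

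**Assumed inputs.** The documents do not give the correlation rho between baseline SUV and its fractional change; I use 0.3, 0.5 and 0.7. Nor do they say how well baseline SUV separates the groups; I use AUC 0.75, a shift of √2·Φ⁻¹(0.75) = 0.95 SD. The 6:24 split is also assumed, to show the effect of few responders.

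**Model.** Baseline b is normal with the group shift above. Change is x = rho·b + √(1 − rho²)·e, plus a group effect where stated. The unadjusted test is the rank-sum test on x. The adjusted test is the group term from a regression of rank(x) on group and rank(b).

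**1. Change carries nothing beyond baseline (no group effect, baseline AUC 0.75).** Percentage of trials significant:

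| rho | 15:15 unadjusted | 15:15 adjusted | 6:24 unadjusted | 6:24 adjusted |
|---|---|---|---|---|
| 0.3 | 10–12% | about 5–6% | about 9% | about 5% |
| 0.5 | about 22% | about 5–6% | about 15% | about 5% |
| 0.7 | about 39% | about 5–6% | about 25% | about 5% |

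The mechanism is simple. At rho 0.5, a baseline shift of 0.95 SD passes 0.5 × 0.95 = 0.48 SD on to the change score, and the unadjusted test picks this up. A baseline difference of 1 SD gives similar results at 15:15: 12%, 24% and 42%.

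**2. Power, with the marginal effect fixed at p = 0.82 and rho = 0.5.**

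| Baseline SUV | Split | Unadjusted | Adjusted |
|---|---|---|---|
| Same in both groups | 15:15 | about 90% | about 96% |
| Same in both groups | 6:24 | about 73% | about 84% |
| AUC 0.75, explains part of the difference | 15:15 | about 91% | about 62% |
| AUC 0.75, explains part of the difference | 6:24 | about 73% | about 42% |

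Adjustment can move power either way. Where it lowers power, the lost signal was already available before treatment.

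**The case against.** - **The stated objective is answered.** Objective 2.1.1 asks whether fractional change differs between groups, and Section 7.1 describes the primary endpoint as an association. The rank-sum test addresses both. Section 1.1 calls the information preliminary, and Section 1.3 places the treatment decision in the future. All of this stands, and it is why the primary test should stay. It does not close the gap between an association and a statement about what the mid-treatment scan contributes.
- **Part of the information may be reported anyway.** Section 7.3 summarises each image measure by response group, tests all quantitative measures and correlates them. Read broadly, that could show a baseline imbalance and the baseline–change correlation. Baseline is also the denominator of the primary measure. This stands too, but none of it puts baseline and change in one analysis of response.
- **The inputs are assumed.** Neither rho nor the baseline AUC is in the documents. Nor does a correlation that comes only from baseline measurement noise do the harm: with true fractional change unrelated to group, baseline AUC 0.70–0.75 and assumed noise of 10–25% (log-SUV SD 0.5), the unadjusted test rejected in 4–5% of trials. False credit needs a real baseline–change relation together with a group imbalance.
- **A reader might infer that the plan wastes power by not adjusting.** That reasoning belongs to randomised groups with balanced baselines. Here adjustment changes the question as well as the precision, and the power results above go in both directions.
- **A reader might also infer that every prediction statement should depend on an adjusted test.** In a 30-patient pilot, that would make a different question, for which the study was not powered, decide the interpretation of the primary result. The documents do not require it.

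**Conclusion.** The concern holds as a gap in interpretation and incremental value. It is not an error in the primary test. Section 7.3 cannot separate information gained at mid-treatment from information already in the pre-treatment scan.

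The size depends on two unknowns. At 15:15 with baseline AUC 0.75, a change score that adds nothing is still significant in about 10–12% of trials at rho 0.3 and about 39% at rho 0.7. If baseline SUV is balanced between the groups or unrelated to change, there is no systematic false credit. The documents support neither a general loss of power nor the view that a significant rank-sum result would be invalid: it would show association, as objective 2.1.1 asks.

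**What to change.** In Section 7.3:

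1. Keep the rank-sum test of fractional change in mean SUV as the primary analysis.
2. In the exploratory logistic analysis, add baseline mean SUV to the candidate measures. Separately from the subset selection, pre-specify two models: baseline mean SUV alone, and baseline mean SUV plus fractional change to mid-treatment. Report the likelihood-ratio test between them and the difference in leave-one-out cross-validated AUC.
3. Report a rank ANCOVA (ranked fractional change on response group and ranked baseline mean SUV) as a supporting analysis, not as a condition for interpreting the primary result.
4. State that a significant rank-sum result shows association, and that any statement that the mid-treatment scan adds to the pre-treatment scan rests on the comparison in step 2.

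The cost is some SAP wording and a few lines of code, with no new data, visits or patients. With 30 patients and possibly few responders (six at a 6:24 split), the comparison will be imprecise. It should be labelled exploratory, and a non-significant result should not be read as showing that the mid-treatment scan adds nothing.

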### **2.3 Exploratory Objectives**

- 2.3.1** To assess the utility of combined, simultaneous positron emission tomography (PET mean SUV) and magnetic resonance imaging (MRI tumor size), in early prediction of response to neoadjuvant radiation therapy in the treatment of high-grade sarcomas at mid-treatment and post-treatment.
- 2.3.2** Examine the utility of using maximal SUV in place of mean SUV in prediction of response

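### Exploratory objective 2.3.2 asks about maximal SUV in place of mean SUV, but section 7.3 plans no estimate of the difference in predictive ability between the two

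*Combined protocol and SAP*

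**What the plan says.** Section 2.3 lists as its second exploratory objective: "Examine the utility of using maximal SUV in place of mean SUV in prediction of response". It names no time point. The first exploratory objective, which concerns mean SUV and MRI size, covers both mid-treatment and post-treatment.

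Section 7.3 computes fractional changes for three measures, and maximum SUV is one of them ("Quantitative imaging measures (mean SUV, maximum SUV, MRI-based tumor" volume). It then plans:

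- a separate group comparison for each: "Differences in all quantitative measures between the response groups will be assessed with the non-parametric Wilcoxon Rank Sum test";
- agreement between measures: "correlations between quantitative measures will be determined using the non-parametric Spearman's rank correlation coefficient and Pearson product-moment correlation coefficient";
- a logistic classifier "utilizing various PET SUV and MRI-based imaging measures (in terms of change from pre-treatment to mid-treatment) as covariates";
- selection: "All subsets selection with BIC will be used to determine the best combination of PET and MRI imaging measures to predict binary response";
- performance: "empirical measures of predictive performance such as leave-one-out cross validation and Receiver-Operating-Characteristic (ROC) curves".

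Section 7.1 adds that combined PET and MR will be compared with each metric alone. It plans no such comparison of maximal with mean SUV. Section 7.2 takes P(X>Y) as the effect size, with 0.82 as the planning value.

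**The concern.** Whether one measure can replace another is a question about a difference: how well does maximal SUV separate responders from non-responders, relative to mean SUV, in the same patients and scans? The planned analyses come close to this but do not answer it.

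- Two rank-sum tests give two p-values, each against no association. One below 0.05 and one above is not evidence that the measures differ.
- A correlation shows how alike the measures are, not whether one predicts as well as the other.
- BIC selection seeks a good combination of measures. Cross-validation and AUC are described as performance measures for the prediction model. No AUC difference between the SUV measures, and no interval for one, is planned.

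Section 1.1 says that the results may feed effect-size and sample-size estimates for later studies. Without a stated analysis for 2.3.2, a reader choosing an SUV measure has only two p-values and a BIC choice to go on, and both can differ by chance alone.

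**Working it through.** **Inputs from the documents.** 30 completers (section 7.2: "Assuming 30 patients complete the study"); planning P(X>Y) = 0.82; Type I error 0.05. Section 7.2 writes both response groups with the same n, which implies 15:15.

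**Assumptions, because the documents give no figure.** Within-group correlation between the two SUV changes (0.5 to 0.95); AUC below 0.82 (0.75, 0.70); unequal splits (down to 6:24); two-sided rank-sum testing; for the BIC check, one MRI covariate with AUC 0.65.

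**Step 1: the plan's own power.** Noether's formula with equal groups is power = Φ(√(12 × 0.5 × 0.5 × 30) × |0.82 − 0.5| − z) = Φ(9.487 × 0.32 − z) = Φ(3.036 − z). Two-sided (z = 1.960) this gives Φ(1.076) = 85.9%. One-sided (z = 1.645) it gives Φ(1.391) = 91.8%. Simulating the two-sided rank-sum test on shifted normal data at 15:15 gives about 91%. The simulation therefore agrees with the stated power of about 90%.

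**Step 2: two measures that are truly equally good.** Each measure is normal with unit variance, and responders are shifted by √2 × Φ⁻¹(AUC), so both have the same AUC. 20,000 trials were run per scenario. The table gives the share of trials in which exactly one of the two tests is significant:

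| Split | AUC | corr. 0.5 | 0.8 | 0.9 | 0.95 |
|---|---|---|---|---|---|
| 15:15 | 0.82 | 12.7% | 8.7% | 6.8% | 4.8% |
| 6:24 | 0.82 | 28.9% | 18.9% | 14.0% | 9.7% |
| 15:15 | 0.75 | 31.1% | 19.9% | 14.6% | 11.0% |
| 6:24 | 0.75 | 34.8% | 22.0% | 16.0% | 12.2% |

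Hand check of the first cell: each test has power 0.910 and both are significant in 0.846, so exactly one is 2 × (0.910 − 0.846) = 0.128, against 0.127 simulated. At AUC 0.75 with splits from 15:15 to 6:24, the rate is 24–27% at correlation 0.7 and 15–17% at 0.9.

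**Step 3: BIC, if both SUV measures are candidates.** In 600 simulated trials per scenario with splits from 15:15 to 6:24, all-subsets BIC kept exactly one of the two in 81–95% of trials at AUC 0.82 and in 44–72% at AUC 0.70. Which one it kept was about 50:50.

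**Step 4: the direct comparison.** A paired DeLong test at 0.05 calls the equal measures different in 1.4–6.0% of trials, over splits from 15:15 to 6:24, AUC 0.70–0.82 and correlation 0.5–0.95.

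For correlations of 0.7–0.9 over these splits and AUCs, the standard deviation of the paired AUC difference is about 0.04 to 0.10. The half-width of a 95% interval is then 1.96 × 0.041 = 0.08 at the precise end (15:15, AUC 0.82, correlation 0.9) and 1.96 × 0.10 = 0.20 at the other.

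**The case against.** Four counter-arguments deserve an answer.

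**The plan declares nothing.** A reader might infer that the trial will call the measures different whenever one p-value is below 0.05 and the other is not, or whenever BIC keeps only one. The documents contain no such rule, and the BIC step serves the choice of a PET and MRI combination. This stands: the rates above describe a misreading that the plan leaves open, not an error rate of the plan.

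**The plan does more than test each measure alone.** It also has correlations, cross-validation and AUC, and the agreement between the two measures is relevant to substitution. This stands as far as it goes, but none of these is an estimate of the difference in prediction. That both measures enter the BIC search is also an inference. The text refers to various PET SUV measures without listing them, although mean and maximum are the only ones that section 7.3 names.

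**Objective 2.3.2 may only mean repeating the analysis with maximal SUV substituted.** That is a fair reading. Even then the reader ends with two results and must compare them, so the difference and its uncertainty are still needed.

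**If the measures are equally good, choosing either loses no discrimination.** This is correct, and it limits the harm shown here to a false impression of a difference. The cost of choosing the worse of two unequal measures was not calculated.

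**Conclusion.** The gap is real but small. Objective 2.3.2 has no analysis that estimates the quantity it asks about, although the paired data will be collected.

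It would be tempting to say that chance differences will be frequent. For the rank-sum tests, the plan's own assumptions (0.82, equal groups) do not support that: the rate is about 5–13% for correlations from 0.95 down to 0.5. It reaches about 15–27% only with an assumed AUC of 0.75 (correlations of 0.7–0.9), and it also rises at 0.82 if responders are few. The near-random choice by BIC is the stronger effect, but it depends on both measures being candidates.

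Nor should the paired analysis be expected to settle the question. With an interval of about ±0.08 to ±0.20 on the AUC scale and no margin in the plan, 30 patients can describe the difference but cannot establish interchangeability.

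The objective is exploratory in a study meant to give preliminary information, so this is a low-priority improvement.

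**What to change.** Add to section 7.3, for objective 2.3.2:

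- Report the difference in AUC, which is the P(X>Y) of section 7.2, between maximal-SUV and mean-SUV fractional change in the same patients. Do this at mid-treatment and at post-treatment, with the direction of both AUCs fixed in advance.
- Give a 95% interval by DeLong's method or by a bootstrap that resamples patients.
- State that this estimate addresses 2.3.2, and that the two rank-sum p-values and the BIC selection do not.
- Label it descriptive, and say that 30 patients cannot show the measures to be interchangeable.

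Leave the candidate set for the BIC search as planned. Restricting it to one SUV measure at a time is a separate and debatable modelling choice that this point does not require.

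The cost is a few sentences and a short extra analysis. No additional patients, scans or visits are needed. The one caution is that with very few responders the interval becomes unreliable: at an assumed 3:27 split, the DeLong comparison of equal measures rejects in 1.8–8.7% of trials over AUC 0.70–0.82. The number of responders should be shown beside it.
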